PROTOCOL TITLE: Does the VerTouch Device Improve Insertion Site Identification for Lumbar Neuraxial Procedures when Compared to Palpation or Ultrasound Guided Site Selection? A Prospective Randomized Controlled Trial

PRINCIPAL INVESTIGATOR:

[name].
Department of Anesthesiology
[contact]
[contact]

VERSION DATE: 1.1 03/26/2021

STUDY SUMMARY:

Investigational Agent(s) (Drugs or Devices)	Intuitap VerTouch Device
IND / IDE / HDE #	
Indicate Special Population(s)	Children Children who are wards of the state Adults Unable to Consent Cognitively Impaired Adults Neonates of Uncertain Viability  Pregnant Women Prisoners (or other detained/paroled individuals) Students/Employees
Sample Size	120
Funding Source	Intuitap Medical
Indicate the type of consent to be obtained	 Written Verbal/Waiver of Documentation of Informed Consent Waiver of HIPAA Authorization Waiver/Alteration of Consent Process
Site	Lead Site (For A Multiple Site Research Study) Data Coordinating Center (DCC)
Research Related Radiation Exposure	Yes  No
DSMB / DMC / IDMC	Yes  No

OBJECTIVES:

Is there an identifiable difference in the number of insertions and redirections of the needle for a lumbar neuraxial procedure when the VerTouch device is used, instead of palpation (current gold standard) or ultrasound guidance (US), for the identification of the procedural insertion site?

Null Hypothesis:

There is no difference in the number of insertions and redirections of the needle for a lumbar neuraxial procedure when the VerTouch device is used.

BACKGROUND:

Literature:

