In this project we aim to compare the VerTouch device to palpation and US techniques used to identifying the anatomic landmarks and optimal location for neuraxial access. In a previous feasibility study completed here at Northwestern University (NU) in Prentice Women's hospital (stu#: 00207454), the researchers showed that when VerTouch was used to mark a site prior to the neuraxial procedure, and the site marked was eventually used for the procedure, the success rate of the procedure with minimal needle manipulation was greater than historical data for the gold standard palpation technique. Additionally, the provider confidence in the information provided by the device was greater than 95% (abstract and/or submitted manuscript for this study can be provided on request). The proposed RCT herein will be a prospective comparison

of the now proven VerTouch device to the gold standard of palpation and the commonly cited US techniques.

SIGNIFICANCE:

Thousands of neuraxial procedures are completed daily with over 12,000 done at Prentice Women's hospital last year. These procedures are not without difficulty and complication. The gold standard of palpation and blind advancement of the needle toward the spine can result in multiple insertions of the needle into the skin and redirections of the trajectory of that needle after insertion to avoid the bones of the spine protecting the spinal column. These insertions and redirections are not only time consuming while the patient is in an uncommon position, but they also cause discomfort and possibly lasting pain days after the procedure. In addition to the patient dynamics, when anatomical or positioning issues result in difficult neuraxial procedures the common teaching is to attempt US guided access. Unfortunately, not many proceduralist are trained in this modality and the additional materials needed to perform the procedure with US take time to gather and further prolong the procedure. Additionally, though the cost of US technology is getting more reasonable, it is still rather expensive and a barrier to utilization by many facilities around the country and the world. Often, after many attempts, the proceduralist accepts failure of the procedure and refers the patient to the interventional radiology (IR) or pain medicine specialist for completion of the procedure using radiation to visualize the spine. Note, this is not an option for pregnant women who are not eligible for radiation due to fetal concerns.

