The VerTouch offers a non-invasive, untethered, and non-radiation producing device that allows for the visualization of the underlying structures of the spine to determine ideal needle placement for neuraxial procedures. The output on the screen can also be visualized by other providers or senior proceduralist for assistance with best course of action for the procedure. The device does not cause discomfort to the patient and does not require any additional materials to be functional.

This study has the potential to show that the VerTouch is more effective than palpation and as effective as US at defining the location for neuraxial procedure initiation and eventual success. If the VerTouch device is capable of improving the consistency of success of neuraxial procedures, while minimizing need for costly and cumbersome US technology and decreasing referral to radiation requiring procedures, the benefit to patients and proceduralists would be exponential.

STUDY ENDPOINTS: The primary endpoint is the combined total number of insertions or redirection of the needle being used for the procedure.

The endpoint is when all the subjects for each arm have been recruited and completed study procedures.

STUDY INTERVENTION(S) / INVESTIGATIONAL AGENT(S):

We will use the VerTouch device which we have shown to be a non-significant risk device (IDE). It is comprised of a non-invasive pressure sensor that is gently pushed against the back, with a screen that reads out the pressure being applied across the device. Areas of higher pressure are suggestive of bony areas, whereas areas of lower pressure are more likely tissue. The application of the device to the body is less obtrusive than ultrasound, which is commonly used, because this device does not use any gel or other medium.

The device will be stored in a locked space only accessible to the proceduralist or research personnel authorized to prepare the device for use. The device is self-contained and powered by an internal rechargeable battery. The device will only be at the bedside for those subjects that

have been recruited to participate. In order to maintain blinding, even if the device is not used for the recruited patient it will be at the bedside to ensure the observers are not un-blinded.

PROCEDURES INVOLVED:

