Patients can withdraw from the study at any time and their data will be deleted, and in no way will this impact their care since the study explicitly does not affect the standard of care. The study team will notify the PI by secure NM or NU email if a subject withdraws from the study.

RISKS TO PARTICIPANTS

No significant risk to the patient exists with the utilization of the VerTouch device. The materials on the device that come in contact with the patient are similar or the same as those that make up the US probes used in current state. The device is non-invasive and does not generate radiation or any other emission that would affect the patient's skin or underlying tissues.

POTENTIAL BENEFITS TO PARTICIPANTS

While there is no direct benefit to participants, we do hope that this will benefit pregnant and non-pregnant patients in the future who are undergoing neuraxial procedures. Our previous feasibility study did suggest that the use of the VerTouch may represent an improvement on the current gold standard of palpation.

DATA MANAGEMENT AND CONFIDENTIALITY

Based on the feasibility study data collected and published earlier this year at our institution the incidence of first insertion success when utilizing the VerTouch device is 90.1%. Using historical data from studies comparing Ultrasound to Palpation the first insertion success rates are 62.9 and 43.6%, respectively. When utilizing the anticipated incidence of first insertion success for the VerTouch device and Ultrasound to complete a sample size calculation, given Type 1 and Type 2 error are 0.05 and 80%, respectively, each group must contain 38 patients. Therefore, when including the control "palpation" group, the total population needs to be 114 patients. We plan to recruit 120 patients, 40 in each group, to ensure appropriate sample size and allow unknown possible exclusions of recruited patients."

All photographs will be maximally zoomed in. If it is impossible to take a video that does not include identifying marks on the back (i.e. a birthmark or tattoo) no image will be taken. Data will be stored in REDcap using NM password protected computers for data entry.

Data in REDcap is backed up nightly using NM servers which are only accessible to the NM IT administrator. Data in REDcap and pictures/videos will be destroyed 5 years after the completion of the study.

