Statistical analysis: Data will be compared between groups using the chi2 statistic or the Fisher's exact test. A $P < 0.05$ will be required to reject the null hypothesis.

PROVISIONS TO MONITOR THE DATA TO ENSURE THE SAFETY OF PARTICIPANTS
N/A (minimal risk study)

PROVISIONS TO PROTECT THE PRIVACY INTERESTS OF PARTICIPANTS

Patients in this study, whether undergoing neuraxial access for a disease-state or for the treatment of labor pains, will certainly be under some amount of stress. Having a needle placed into one's back, as is the case for neuraxial procedures, can be stress provoking. Extra care will be taken to approach them during a quiet moment when the clinical team has finished their evaluation. It will be emphasized that in no way will this impact their care, and in fact can help future patients undergo these procedures more quickly and safely to minimize their stress.

COMPENSATION FOR RESEARCH-RELATED INJURY
N/A

ECONOMIC BURDEN TO PARTICIPANTS

There is no cost to the patient to be in this study.

CONSENT PROCESS

Consent will take place in Prentice Women's Hospital 8th floor Labor and Delivery unit at a time mutually convenient to the clinical team, patient, and research team. Subjects will also be recruited from Galter, Lavin and Feinberg pavilions (numerous medical units). They will be offered to contemplate their participation up until 10 minutes prior to the time of their neuraxial procedure (if any less than 10 minutes were available for application of the VerTouch device prior to the clinical procedure, this would risk rushing the clinical procedure). REDcap electronic consent will be utilized to decrease the number of times the paper consent would be touched. Multiple

times throughout the process, the participant will be reminded that this in no way affects their standard of care and that participation can be withdrawn at any time.

NON-ENGLISH SPEAKING PARTICIPANTS

N/A

WAIVER OR ALTERATION OF CONSENT PROCESS

N/A

PROTECTED HEALTH INFORMATION (PHI AND HIPAA)

Does the study involve the creation, use, or disclosure of Protected Personal Health Information?

- Will a HIPAA Authorization be obtained from for all participants? Yes
-
- Name
- Age (years)
- Date of procedure
- Telephone numbers
- Medical Record Numbers
- Email address

QUALIFICATIONS TO CONDUCT RESEARCH AND RESOURCES AVAILABLE

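### The declared primary endpoint is a count of insertions plus redirections, but the sample size is for binary first-insertion success and the named tests are tied to no variable

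*Combined protocol and SAP*

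**What the plan says.** The protocol uses one variable to state its question and another to size the trial.

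- **Null hypothesis (OBJECTIVES):** "There is no difference in the number of insertions and redirections of the needle for a lumbar neuraxial procedure" when the device is used.
- **Primary endpoint (STUDY ENDPOINTS):** "The primary endpoint is the combined total number of insertions or redirection of the needle being used for the procedure". No other outcome is declared.
- **Data collection (PROCEDURES INVOLVED, Randomization):** a blinded observer collects the outcomes. Where video is used instead, the reviewer counts redirections and reinsertions.
- **Sample size (DATA MANAGEMENT AND CONFIDENTIALITY):** "When utilizing the anticipated incidence of first insertion success for the VerTouch device and Ultrasound to complete a sample size calculation", the result is 38 per group, raised to 40 (120 in total). The VerTouch rate is 90.1%, from the feasibility study. For the other arms: "Using historical data from studies comparing Ultrasound to Palpation the first insertion success rates are 62.9 and 43.6%, respectively".
- **Analysis (Statistical analysis paragraph):** "Data will be compared between groups using the chi2 statistic or the Fisher's exact test", at P < 0.05. No variable, cut-point or contrast is given.

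Both contrasts are of interest. SIGNIFICANCE says: "This study has the potential to show that the VerTouch is more effective than palpation and as effective as US".

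**The concern.** Endpoint, sample size and test should all refer to one variable, and here they do not. The sample size paragraph supplies a single binary variable, and the two named tests suit a binary variable. The most natural reading is therefore that the trial will be judged on first-insertion success. That outcome is not declared as an endpoint. The protocol also does not say whether a first insertion that needed redirection is a success, although redirections are half of what the declared endpoint counts.

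Two things follow. The declared count has no analysis suited to an ordered count. And the 80% power, the only justification for 120 patients, belongs to another variable. The choice between variables would remain open when results are available, and a reader could not tell which result was meant to be primary.

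**Working it through.** **1. Reproduce the plan's figure.** Inputs from the sample size paragraph: p1 = 0.901, p2 = 0.629, alpha 0.05, power 80% (the text labels the 80% as Type 2 error; I read it as power). Sidedness is not stated; I assume two-sided. The pooled formula, with p̄ = (0.901 + 0.629)/2 = 0.765, is

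n = [1.960·√(2p̄(1−p̄)) + 0.842·√(p1(1−p1) + p2(1−p2))]² / (p1−p2)²

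= [1.960·√0.3596 + 0.842·√0.3226]² / 0.272² = (1.175 + 0.478)² / 0.0740 = 36.9, so 37 per group against 38 stated. The figure reproduces for first-insertion success.

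**2. Power of the two named tests on that binary outcome.** Summing the binomial probabilities of every 2×2 table with P < 0.05:

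| Per group | Chi-square, uncorrected | Fisher |
|---|---|---|
| 38 | 82.9% | 75.7% |
| 40 | 84.9% | 78.5% |

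The choice between the two tests alone decides whether power is above or below 80%.

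**3. Power for the declared count.** The documents give no mean, spread or effect size for insertions plus redirections in any arm, so none can be derived. The following only illustrates the range. All count distributions are assumed; there are 40 per arm and a two-sided Wilcoxon rank-sum test, and power is simulated.

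| Assumed meaning of success and model | vs ultrasound | vs palpation |
|---|---|---|
| Success = total count of 1; count is 1 + negative binomial, size 0.3 to 3 | 86–89% | over 99% |
| Success allows redirections; equal redirections per insertion, mean 0.5 / 1 / 2 | 52 / 42 / 36% | 96 / 92 / 87% |
| As above, redirections 30% lower with VerTouch | 75–76% | 98–99% |
| Success allows redirections; equal redirections per patient, mean 0.5 / 1 / 2 | about 46 / 30 / 17% | about 94 / 81 / 55–58% |

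In the last three models the number of insertions is geometric with the protocol's success rates. The ranges are not bounds: with a mean of 3 redirections per patient, power against ultrasound is about 12%. If success means no further needle manipulation, the count has roughly the sized power. If success allows redirections that are equally frequent across arms, they add noise and power falls.

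**4. Chi-square applied to the count itself.** Under the first model, against ultrasound, a chi-square on the uncollapsed table has 39–69% power. Grouping the counts as 1, 2 and 3 or more gives about 79–87%, so the loss comes mainly from sparse cells and is largely avoidable.

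**5. The counting convention.** STUDY ENDPOINTS counts insertions, so a clean first pass scores 1. The video procedure counts reinsertions, so the same pass could be recorded as 0. A definition of success by total count depends on which applies.

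**The case against.** The strongest reply is that the sample size and analysis paragraphs, read together, plainly intend a binary analysis: one binary variable with rates for all three arms, and two tests that fit it. The arithmetic is right for that variable. I accept this as the likely intention, but no sentence says so, and the declared endpoint remains the count.

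Four stronger readings are tempting and are not supported.

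- **That the trial is underpowered for its endpoint.** The documents give no count distribution, and some plausible assumptions give power near or above 80%.
- **That the stated null hypothesis would go untested.** If success means no further needle manipulation, a chi-square on it is a valid, coarser test of that null, with about 85% power against 86–89% for the rank test. Nor can one say that success was never defined. BACKGROUND says of the feasibility study that "the success rate of the procedure with minimal needle manipulation was greater than historical data for the gold standard palpation technique", and of its report that "abstract and/or submitted manuscript for this study can be provided on request". The definition is missing from this protocol; it may exist there.
- **That a cut-point would be picked after seeing the data, inflating type I error.** The plan's silence permits this, but no passage proposes it.
- **That the palpation comparison is safe in any case.** This fails if redirections accrue equally per patient: power falls to about 55% at a mean of 2.

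**Conclusion.** The mismatch stands on the text alone, and no section reconciles it. The stated power attaches to first-insertion success, an undeclared outcome that this protocol does not define with respect to redirections. The declared count has neither a suitable named analysis nor an established power. The plan is wrong as written and should be corrected before data are seen.

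The exact figures (37 against 38 per group; 85% and 78% at 40 per group) rest only on the protocol's rates and a two-sided 0.05 level. The ranges for the count (about 17% to 90% against ultrasound, about 55% to over 99% against palpation) rest on assumed distributions. They show how strongly the answer depends on what success means and how often redirections occur; they do not estimate the trial's power.

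**What to change.** Choose one option before data are seen.

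**(a) Keep the count as primary.**
- Replace chi-square/Fisher for it with a method that uses the ordered count, for example a Wilcoxon rank-sum test stratified by the pregnant and non-pregnant cohorts.
- Name VerTouch vs ultrasound, the sized contrast, as the primary comparison. If palpation is to be co-primary, state a multiplicity rule.
- State that 38 per group and 80% power apply only to first-insertion success, and give power for the count at 40 per group under stated assumptions.

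**(b) Declare first-insertion success primary.**
- Define it with respect to redirections in the way the 90.1% and 62.9% were measured, checking the feasibility report and the source of the ultrasound rate. If the two were measured differently, restate the sample size.
- Name one test. At 40 per group, uncorrected chi-square keeps power above 80%; Fisher gives about 78%.
- Analyse the count as secondary with an ordered method.

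Under either option, state whether a clean first pass is recorded as 0 or 1.

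The cost is protocol wording. Option (a) may yield a power statement less favourable than 80%, and option (b) changes the declared endpoint. Insertions and redirections are already being counted, so neither needs new outcome data or more patients.
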